#### 14.5.1 Subgroup analysis for DOR

DOR according to RECIST 1.1 as adjudicated by IRC will also be evaluated on all subgroups as defined in Section [8.2](#). This will be repeated for Japanese participants including only the ADA and nAb status subgroup.

Participants with missing subgroup category will not be included in the related subgroup analysis. Those subgroups analyses will be supported by forest plots (based on DOR rates at 6-month and 12-month).

## 14.6 Durable Response (Secondary Endpoint)

Analysis (Analysis Population)	Derivation	Statistical Analysis Methods	Missing data handling
Secondary endpoint: Durable Response Rate (DRR)			
Secondary analysis (ITT)	Number of participants having a DOR of at least 6 months, out of the total number of participants	DRR will be provided with a two-sided 95% CI using the Clopper-Pearson method (exact CI for a binomial proportion as computed by default by the FREQ procedure using the EXACT option).	Participants with missing baseline and post-baseline tumor assessments will be defined as non-evaluable, and considered as having no response.

**Durable Response Rate (DRR)** is defined as the number of participants having a DOR of at least 6 months, out of the total number of participants.

The DRR will be provided with a two-sided 95% CI using the Clopper-Pearson method (exact CI for a binomial proportion as computed by default by the FREQ procedure using the EXACT option).

DRR will be described according to RECIST 1.1 as measured by the IRC and the Investigator.

### 14.6.1 Subgroup analysis for DRR

DRR according to RECIST 1.1 as adjudicated by IRC will also be evaluated on all subgroups as defined in Section 8.2. This will be repeated for Japanese participants including only the ADA and nAb status subgroup.

Participants with missing subgroup category will not be included in the related subgroup analysis. Those subgroups analyses will be supported by forest plots.

## 14.7 Delayed Response

**Delayed response** will be defined as a documented objective response [CR or PR] that occurred after the initial progression of disease. For those participants, the duration of delayed response (DOdR) will be defined as:

DOdR = (date of end of objective response – date of objective response + 1)/30.4375 (months).

with end of response being the earliest date between PD occurring after response, death, start of new anticancer treatment or cut-off date.

Two listings for participants having a delayed response according to RECIST 1.1 as measured by IRC will be described will be provided:

- For tumor assessment including: participant identifier, age, sex, race, date of first and last study intervention, date(s) of imaging, sum of lesion diameters, percent change in target lesions from baseline, and overall response.

- For duration of response including: participant identifier, age, sex, race, date of first and last study intervention, date/study day of first PD, date/study day of first response (CR or PR), ongoing response at cutoff date (Y/N), date/study day of end of response (with reason for end of response being PD, death, new anticancer treatment), duration of delayed response.

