### **7.1.2.3 Continuation of Study Intervention After Local Treatment of Disease Progression**

If disease progression is due to brain metastasis, participants may continue study interventions after local treatment of the brain lesions provided that the above criteria are met in addition to the following:

- PD is verified by the IRC.
- Brain metastases have been treated locally and are clinically stable for at least 2 weeks prior to reinitiation of study interventions.
- There are no ongoing neurological symptoms that are related to the brain localization of the disease (sequelae that are a consequence of the treatment of the brain metastases are acceptable).
- Participants must be either off steroids or on a stable or decreasing dose of  $\leq 10$  mg daily prednisone (or equivalent).
- Benefit-risk assessment to continue study intervention is favorable after consideration of any alternative treatment options as assessed by the Investigator.

In addition, if disease progression is mainly due to a metastatic lesion, which in the opinion of the Investigator may be treated with radiotherapy or surgically removed, participants may continue study interventions after the local treatment of such a lesion provided that:

- PD is verified by IRC.
- It has been at least 2 weeks and the participant has fully recovered from the surgery or radiotherapy.
- Benefit-risk assessment to continue study intervention is favorable after consideration of any alternative treatment options as assessed by the Investigator.

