### Best overall response (BOR)

Best overall response will be assessed based on the tumor response at different evaluation timepoints from the first study intervention until the first documented disease progression for RECIST criterion. Only tumor assessments performed before the start of any further anticancer treatment will be considered in the assessment of BOR. Clinical deterioration will not be considered as documented disease progression.

BOR can be defined as confirmed or unconfirmed, both definitions are provided below.

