		
Censoring rules (details provided in body text):
 
 
- No event (PD or death)
 
- No baseline and/or post-baseline assessment
 
- Start of new anticancer treatment
 
- Event after two or more subsequent missing response assessments
 

Sensitivity Analysis 1: PFS counting all events (PD and death) regardless of the start of a new anticancer therapy and ignoring the number of missing evaluable tumor assessments before progression or death

Sensitivity Analysis 2: PFS as assessed by the Investigator

**Progression-Free Survival (PFS)** time is defined as the time from first administration of study treatment until the first documentation of progression of disease (PD) or death due to any cause, whichever occur first.

PFS = (date of PD or death or censoring – date of first administration of study treatment + 1)/30.4375 (months).

The following censoring rules will also be applied for the PFS computation:

- Participants with no event (PD or death) will be censored on the date of the last adequate tumor assessment
- Participants who do not have a baseline tumor assessment or who do not have any evaluable post-baseline tumor assessments will be censored at the date of first administration of study treatment unless death occurred on or before the time of the second planned tumor assessment (i.e. 16 weeks) in which case the death will be considered an event.
- Participants who start new anticancer treatment prior to an event will be censored on the date of the last evaluable tumor assessment before anticancer therapy is given.

Note: any systemic anticancer therapy, any anticancer surgery and any anticancer radiotherapy with exception of palliative bone radiotherapy will be considered as new/subsequent anticancer therapy and will lead to censoring.

- Participants with an event after two or more subsequent missing response assessments (i.e. no assessments in 112 days during the first 12 months of follow-up or 168 days after the first 12 months of follow-up) will be censored on the date of the last evaluable tumor assessment.

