The analysis of DOR will be performed with a Kaplan-Meier method (product-limit estimates) and a summary of associated statistics will be presented including corresponding two-sided 95% CIs. The CIs for the median will be calculated according to Brookmeyer and Crowley (1982) and CIs for the survival function estimates will be derived using the log-log transformation according to Kalbfleisch and Prentice (1980) (CONFTYPE=loglog default option in SAS PROC LIFETEST). The estimate of standard error will be computed using Greenwood's formula.

DOR rates with their CI at 3, 6, 9, 12 and 24 months will be presented, as well as the number of participants at risk and failed.

The time to and duration of response per participant having a confirmed objective response (including delayed response, see Section [14.7](#) below) will be displayed in swimmer graphs. Kaplan-Meier figures will also be provided.

Listings will be provided with the following information: participant identifier, age, sex, race, date of first study treatment administration, date of first response, date of last tumor assessment, censored (Y/N), date of event/censoring, event/censoring reason and duration of response.

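### SAP 14.7 admits a delayed response that follows new anticancer treatment, and its end-date rule then gives that response a zero or negative duration; only descriptive listings and swimmer graphs are affected

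*SAP*

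**What the plan says.** SAP 14.7 has one entry condition: a delayed response "will be defined as a documented objective response [CR or PR] that occurred after the initial progression of disease". The duration in months is the end date minus the response date, plus one day, divided by 30.4375, "with end of response being the earliest date between PD occurring after response, death, start of new anticancer treatment or cut-off date". In that list only progression carries the qualifier that it must come after the response.

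The results go into two listings for IRC-assessed delayed responders, one of tumor assessments and one of durations. SAP 14.5 adds swimmer graphs for participants "having a confirmed objective response (including delayed response", with a pointer to 14.7.

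Other sections do deal with new therapy. For best overall response, SAP 14.1 states: "Only tumor assessments performed before the start of any further anticancer treatment will be considered in the assessment of BOR". PFS censors at new therapy (SAP 14.4, Table 5), and DOR takes over the PFS rules (SAP 14.5). The SAP 14.4 note defines the term broadly: "any systemic anticancer therapy, any anticancer surgery and any anticancer radiotherapy with exception of palliative bone radiotherapy will be considered as new/subsequent anticancer therapy".

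**The concern.** A CR or PR seen after another anticancer treatment has begun cannot be put down to bintrafusp alfa alone. The SAP recognises this for BOR, PFS and DOR, but 14.7 carries no such restriction. New treatment appears there only as something that ends a response, not as something that prevents one from qualifying.

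The first consequence is that a response arising after a later therapy is listed as a delayed response in this trial. The second is that its computed duration can be zero or negative, which is impossible and would have to be resolved by an unplanned programming decision.

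The sponsor has shown interest in such responses. Protocol 2.2 and 4.2 mention one participant among the 30 in the Phase Ib study with a PR ongoing at 7.6+ months after initial progression. The listings should therefore mean what their title says.

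**Working it through.** The plan states no figure for this item, so there is nothing to reproduce. The check applies the 14.7 rule literally.

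**1. Can another section close the gap?** The BOR exclusion works within a window running "from the first study intervention until the first documented disease progression for RECIST criterion". A delayed response lies outside that window by definition. The PFS and DOR censoring rules are not cross-referenced in 14.7, which has its own end rule.

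**2. Which end date can precede the response?** Progression is limited by the text to dates after the response. Death cannot precede it. Data after cut-off are not displayed or summarised (SAP 9), so a listed response cannot fall after the cut-off. The start of new anticancer treatment is the only candidate that can come first.

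**3. Formula.** Let g be the number of days from the start of new treatment to the response. If g is 0 or more and no other end date is earlier, the end date is the treatment start and

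DOdR = (end - response + 1)/30.4375 = (1 - g)/30.4375 months.

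**4. Numbers.** Assumed study days: first PD on Day 57 (the first scheduled scan in Protocol Table 1), PR on Day 113 (the next scan, 8 weeks later), further PD on Day 281, cut-off on Day 400.

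| New treatment starts | g (days) | DOdR (months) |
|---|---|---|
| Day 113 | 0 | (113 - 113 + 1)/30.4375 = +0.03 |
| Day 112 | 1 | 0/30.4375 = 0.00 |
| Day 111 | 2 | -1/30.4375 = -0.03 |
| Day 106 | 7 | -6/30.4375 = -0.20 |
| Day 70 | 43 | -42/30.4375 = -1.38 |
| Day 57 | 56 | -55/30.4375 = -1.81 |

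When no new treatment comes first, the formula behaves properly. With none at all it gives (281 - 113 + 1)/30.4375 = 5.55 months. With treatment on Day 200 it gives (200 - 113 + 1)/30.4375 = 2.89 months.

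**5. Can the case arise?**
- *Stopping study drug and starting another therapy.* Protocol 4.1 and 8.1.1 schedule scans until confirmed progression. The Table 1 note for participants who stop for a reason other than PD says the same. None of them stops scanning at new therapy. A participant with an initial, unconfirmed PD who is on another therapy can therefore still be scanned and read as PR.
- *Local treatment of a progressing lesion.* Under Protocol 7.1.2.3, if a lesion can be irradiated or removed, "participants may continue study interventions after the local treatment of such a lesion provided that" certain conditions are met. Whether this sets a new-treatment date is unclear. The SAP 14.4 note counts surgery and radiotherapy other than palliative bone radiotherapy. SAP 9 (on-treatment period) and SAP 12.5 draw subsequent therapy from eCRF pages for treatment after discontinuation, while SAP 12.3 takes concurrent procedures from a separate page. SAP 14.7 does not say which applies.

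**The case against.** The strongest reply is that no estimate depends on this. Delayed response is not among the visible objectives, and 14.7 plans no rate, confidence interval or test. A reader might infer that the trial's response results are inflated. The documents do not support that: confirmed ORR is protected by the BOR rule, PFS censors at new therapy, DOR follows PFS, and DRR is built on DOR. This part of the reply stands and sets the severity.

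A second reply is that the listings expose the problem. The duration listing shows first PD, first response, end of response and its reason, so a reversed pair of dates would be visible. The main tumor listing in SAP 14.1 also shows the start of subsequent therapy. This weakens any claim that the response is silently credited to study drug. It does not change who qualifies as a delayed responder, and neither 14.7 listing has its own field for the start of new therapy.

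A third reply concerns reach. A reader might take every resection or irradiation under Protocol 7.1.2.3 as a certain negative duration. The documents do not settle that. If only the after-discontinuation pages supply the date, such a participant has no new-treatment date and the duration is not negative, although the response still follows local treatment. The therapy-switch route is also narrow. It needs an unconfirmed PD, another therapy and a later IRC-read response, and the Table 1 note covers only participants who stop for a reason other than PD. The route is still open, because the general scan schedule runs to confirmed progression.

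**Conclusion.** Wrong as written, low severity. Taken literally, 14.7 counts a CR or PR that follows new anticancer treatment. The duration is then 0 at a one-day gap and negative at two days or more; in the Day 70 and Day 113 example it is -1.4 months. For a same-day start it is one day, and for responses with no earlier new treatment the formula works. It would be too strong to say that the formula fails in general.

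The effect is confined to the two IRC listings and the swimmer graphs. The documents give no frequency, and the single Phase Ib case does not show how large a share of the listing would be affected. The study days in the example are assumptions, but the sign of the result depends only on the gap between treatment start and response. The clearest route is a participant who stops study drug, starts another therapy and is still scanned until confirmed PD. Local treatment under Protocol 7.1.2.3 is a route only if on-study surgery or radiotherapy counts as new anticancer treatment.

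**What to change.** In SAP 14.7:

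1. Require the CR or PR to be documented after the initial PD and before the start of any new anticancer treatment, as defined in the SAP 14.4 note.
2. State that this includes surgery, and radiotherapy other than palliative bone radiotherapy, recorded while study drug continues, and not only entries on the after-discontinuation eCRF pages.
3. Limit end-of-response candidates to dates on or after the response.
4. List any CR or PR after new treatment separately, not as a delayed response, and apply the same definition to the swimmer graphs.

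Item 3 alone is not enough. In the example it would replace -1.38 months with 5.55 months, a plausible figure for a response that still followed other treatment. With items 1 and 3 together, the Day 70 participant is not a delayed responder, and any computed duration is at least one day (1/30.4375 = 0.03 months).

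The cost is a short wording change and one added date condition, which may need to draw on the concomitant procedures page. No new data collection is apparent. The downside is possibly fewer delayed responders.

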The last tumor assessment date is defined as the last available and evaluable tumor assessment performed prior to the cut-off date (or prior to end of study, i.e. participants lost to follow-up or who withdraw consent) or prior to subsequent anticancer therapy. If no evaluable tumor assessment is available, this date will be the date of first administration of study treatment.

Censoring rules are also summarized in [Table 5](#).

**Table 5** Censoring Rules for Primary and Sensitivity Analysis of PFS

Situation		Primary Analysis	Sensitivity Analysis 1	Sensitivity Analysis 2
No PD and no death	New anticancer therapy is not initiated	Censored at last tumor assessment*	Censored at last tumor assessment*	Censored at last tumor assessment*
	New anticancer therapy is initiated	Censored at last tumor assessment* before new anticancer therapy	Censored at last tumor assessment*	Censored at last tumor assessment* before new anticancer therapy
No baseline assessment or no evaluable post-baseline assessment	No death or death >16 weeks after start of study treatment	Censored at date of first administration of study treatment	Censored at date of first administration of study treatment	Censored at date of first administration of study treatment
	Death ≤16 weeks after start of study treatment	Progressed at date of death	Progressed at date of death	Progressed at date of death
PD or death	After ≤1 subsequent missing response assessment a	Progressed at date of document PD or death, whichever came first	Progressed at date of documented PD or death, whichever came first	Progressed at date of documented PD or death, whichever came first
	After ≥2 subsequent missing response assessment a	Censored at last tumor assessment* before missing assessments.	Progressed at date of documented PD or death, whichever came first	Censored at last tumor assessment* before missing assessments
	Before started new anticancer therapy	Progressed at date of document PD or death, whichever came first	Progressed at date of documented PD or death, whichever came first	Progressed at date of document PD or death, whichever came first
	After started new anticancer therapy	Censored at last tumor assessment* before new anticancer therapy	Progressed at date of documented PD or death, whichever came first	Censored at last tumor assessment* before new anticancer therapy

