### 14.5 Duration of Response (Secondary Endpoint)

Analysis (Analysis Population)	Derivation	Statistical Analysis Methods	Missing data handling
Secondary endpoint: Duration of Response (DOR)			
Secondary analysis (ITT)	The duration of overall response is measured from the time from first documentation of confirmed objective response (CR or PR) to the date of first documentation of objective progression of disease (PD) or death due to any cause, whichever occurs first. This definition applies only to participants who experienced confirmed objective response. It will be measured according to RECIST 1.1 as measured by the IRC and the Investigator	Kaplan-Meier estimates (product-limit estimates) will be presented together with a summary of associated statistics (median time, 3-, 6-, 9-, 12-, 24-month rate estimates) including the corresponding two-sided 95% confidence intervals. The confidence intervals for the median will be calculated according to Brookmeyer and Crowley (1982) and confidence intervals for the survival function estimates at above defined timepoints will be derived using the log-log transformation according to Kalbfleisch and Prentice (2011) (conftype=loglog default option in SAS Proc LIFETEST). The estimate of the standard error will be computed using Greenwood's formula.	Same censoring rules as for PFS.

**Duration of response (DOR)** is defined for participants with a confirmed objective response, as the time from first documentation of confirmed objective response (CR or PR) to the date of first documentation of objective progression of disease (PD) or death due to any cause whichever occurs first:

DOR = (date of PD or death or censoring – date of confirmed objective response + 1)/30.4375 (months).

The censoring rules for DOR are as described above for PFS (primary definition in [Table 5](#)) in Section [14.4](#).

DOR of confirmed CR/PR according to RECIST 1.1 as measured by the IRC and the Investigator will be described. Considering confirmed CR/PR involve having at least two objective responses, the date of occurrence of the first CR/PR will be used as date of objective response.

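### The duration of a delayed response runs to the data cut-off or to the start of new therapy instead of to the last evaluable scan, so listings and swimmer bars include time no scan documents

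*SAP*

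**What the plan says.** SAP 14.7 defines a delayed response as an objective response that occurs after the initial progression. Its duration is the end date minus the response date plus one day, divided by 30.4375 to give months. The response is taken to end at whichever comes first of a later PD, death, "start of new anticancer treatment or cut-off date". The section does not mention the last tumor assessment, missed assessments, withdrawal or loss to follow-up. It plans two listings. One gives imaging dates and tumor measurements. The other gives the duration, a yes/no flag for a response ongoing at cut-off, and an end reason of PD, death or new anticancer treatment.

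For ordinary DOR, SAP 14.5 states: "The censoring rules for DOR are as described above for PFS". Those rules, in SAP 14.4 and Table 5, are:

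- No event: "Participants with no event (PD or death) will be censored on the date of the last adequate tumor assessment".
- New therapy before an event: participants "will be censored on the date of the last evaluable tumor assessment before anticancer therapy is given".
- PD or death after two or more missed assessments (no assessment in 112 days during the first 12 months, or 168 days later): censored at the last evaluable assessment before the gap.

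SAP 14.4 also fixes the reference date: "The last tumor assessment date is defined as the last available and evaluable tumor assessment performed prior to the cut-off date".

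SAP 14.5 adds that the time to and duration of response, with delayed responses included by reference to 14.7, "will be displayed in swimmer graphs".

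**The concern.** A response is known to persist only as far as the last scan that showed it. Running the duration to the cut-off, or to the start of new therapy, counts time for which there is no tumor assessment. The SAP avoids this elsewhere. PFS and DOR stop at the last adequate scan, OS at the last date known alive (14.8), and the duration of antidrug antibody response, for participants still on treatment and positive at their last assessment, at that assessment (16.4.1). Section 14.7 gives no reason for departing from this.

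Two features of the trial make a gap plausible. Protocol imaging runs until confirmed progression (Protocol 4.1 and 8.1.1). After treatment stops for a reason other than PD, the note to Protocol Table 1 continues scans only until confirmed PD. A participant who responds after confirmed PD while still treated (Protocol 7.1.2.2), and then stops treatment, may have no further scan required. SAP 7.1 and 10.2 also anticipate tumor assessments missed because of COVID-19.

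At stake is how a result of clinical interest is described. The Protocol (2.2 and 4.2) cites one Phase Ib participant with a partial response lasting more than 7.6 months after initial progression, and similar cases here are likely to be reported. In the swimmer graphs, bars built on two duration rules would stand side by side.

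**Working it through.** The documents give no figure for this duration, so there is none to reproduce. The check applies the 14.7 formula with two end dates: the cut-off, and the last on-schedule scan.

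**Inputs**

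- Scan interval: 8 weeks (56 days) to month 12, then 12 weeks (84 days) (Protocol 4.1).
- Month length: 30.4375 days (SAP 9).
- Cut-offs: 9 and 15 months after the last participant's first dose (SAP Table 2).
- Last participant's first dose: 3 January 2020 (SAP 9). This puts the cut-offs at 3 October 2020 (study day 275) and 3 April 2021 (study day 457).

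**Maximum excess with on-schedule scans (visit windows ignored)**

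The excess is (end date − last scan)/30.4375, where the end date is the cut-off or the start of new therapy. It stays below one scan interval:

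- 8-week scans: 56/30.4375 = 1.84 months.
- 12-week scans: 84/30.4375 = 2.76 months.

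**Worked example**

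Assumptions: the last-enrolled participant, PD at the day 57 scan, delayed PR at the day 113 scan, and no later PD, death or new therapy. The scan days are then 57, 113, 169, 225, 281 and 337, and after that 421.

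| Cut-off | Duration by SAP 14.7 | Duration to last on-schedule scan | Excess |
|---|---|---|---|
| Primary (day 275) | (275 − 113 + 1)/30.4375 = 5.36 months | day 225: (225 − 113 + 1)/30.4375 = 3.71 months | 50/30.4375 = 1.64 months |
| Second (day 457) | (457 − 113 + 1)/30.4375 = 11.33 months | day 421: (421 − 113 + 1)/30.4375 = 10.15 months | 36/30.4375 = 1.18 months |

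**If imaging stops without a recorded end event**

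The excess is (cut-off day − last scan day)/30.4375.

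| Last scan | Excess at primary cut-off | Excess at second cut-off |
|---|---|---|
| Day 113 | 162/30.4375 = 5.32 months | 344/30.4375 = 11.30 months |
| Day 169 | 106/30.4375 = 3.48 months | 288/30.4375 = 9.46 months |
| Day 225 | 50/30.4375 = 1.64 months | 232/30.4375 = 7.62 months |

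**How many participants**

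One of 30 Phase Ib participants had such a response. The exact 95% CI for 1/30 is 0.1% to 17%. Applied to 141, that is 141 × 0.001 = 0.1 to 141 × 0.17 = 24, or about 0 to 24 delayed responders. Only those without later PD or death run on to cut-off or new therapy, so the number affected is no larger and probably smaller.

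**The case against.** The strongest reply is that nothing inferential depends on this measure. It feeds two listings and a graph, with no test, Kaplan-Meier estimate or rate. It has its own name and a plainly stated rule. The ongoing flag shows which responses had not ended, and the companion listing gives every imaging date, so a reader could work out the gap. Participants treated beyond progression are still assessed on schedule (Protocol 7.1.2.2), which limits unscanned time on treatment.

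Most of this stands, and it keeps the point small. It does not correct the printed duration or the length of the bar. Nor does 14.7 say how a participant who withdrew or was lost is shown. Neither reason is among the three listed ends, so such a case could appear as ongoing, although the section does not say how the flag is set.

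Three stronger readings are tempting and are not supported:

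- A reader might infer that the excess has no limit. It is capped by the cut-off, and earlier by PD, death or new therapy.
- A reader might infer that the rule always flatters the drug. The excess is never negative relative to scan-documented time, but a response truly continuing at cut-off is understated by either rule.
- A reader might scale 1 of 30 to 141/30 = 4.7, or about 5 affected participants. One case cannot support a point estimate, and that count would include delayed responders whose duration ends in PD or death.

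**Conclusion.** The point holds as a minor inconsistency in a descriptive output. When no PD or death follows, SAP 14.7 adds time that no scan documents: up to about 1.8 or 2.8 months on schedule, and up to the whole gap to cut-off if imaging stopped. In the worked example the latter is 1.6 to 5.3 months at the primary cut-off and 7.6 to 11.3 months at the second. Those ranges rest on assumed scan dates, because the documents contain no participant data. The number affected is unknown.

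A reader might infer that the efficacy results are inflated. The documents do not support that. Confirmed ORR counts only responses before progression (SAP 14.1), and DOR, on which DRR is based, already uses the PFS censoring rules.

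**What to change.** In SAP 14.7, replace the end-of-response rule with the primary PFS/DOR censoring rules of Table 5, counting only PD after the delayed response as the PD event:

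- With no later PD or death, end the duration at the last evaluable tumor assessment before new therapy or cut-off.
- When PD or death follows two or more missed assessments, end it at the last assessment before the gap. Without this part, the swimmer graphs would still mix two rules.
- Mark these durations as censored with a plus sign in the listing and on the bars.
- Have the duration listing show the censoring reason, including new therapy (which stops being an end event), withdrawal and loss to follow-up.

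No new data are needed. The cost is a revised derivation, a small change to the listing specification, and slightly shorter durations for some delayed responders.
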